4.2.1.2. Secondary efficacy (exploratory) endpoints

- Time profile of PaO₂/FiO₂ ratio measured at FiO₂ = 1 during mechanical ventilation at four potential time points: ICU admission (time 0) and then q24 hours, up to extubation or up to 72 hours after ICU admission, whichever occurs earlier. Additional data obtained as per center standard of care will be collected in patients with clinical diagnosis of PGD up to the clinical recovery of the condition.
- PGD score (stratified by single or bilateral transplant), evaluated according to the scoring system described by Christie et al. of the working group on primary lung graft dysfunction in the Scientific Council on Pulmonary Transplantation, International Society for Heart and Lung transplantation (2005; see Appendix 1 for methodological details). Specific planned comparison of PGD scores will be made at four time points: ICU admission (time 0), 24 hours, 48 hours, and 72 hours after ICU admission. In patients with clinical diagnosis of PGD additional scoring will be calculated up to the clinical recovery of the condition from available data as per center standard of care.
- Time to freedom from mechanical ventilation, defined as time between admission to the ICU and the initial time of first extubation (breathing off mechanical ventilation without a tube) which is maintained for more than 24 hours.
- Duration of ICU stay.
- ICU mortality, defined as vital status at the ICU discharge.
- Mortality, defined as any death occurring in the first 30 days post-transplant, regardless of hospital discharge.

- FEV₁ and FVC (stratified by single or bilateral transplant) measured at month 1, 6, and 12 post-transplant.
- BOS score (stratified by single or bilateral transplant) evaluated according to Estenne et al. (2002). BOS score will be measured at month 6, and 12 post-transplant.
- Cumulative acute rejection episodes, biopsy proven, evaluated according to Yousem et al. (1996) at month 6 and 12 post-transplant.
- Patient survival rate evaluated at month 6 and 12 post-transplant.
- Any additional information from BAL/biopsies performed according to standard of care in patients with clinical diagnosis of PGD will be collected up to the clinical recovery of the condition.

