### 9.5.2.2 PGD score

Analysis of PGD score will be performed separately at time 0 and at 24, 48 and 72 hours after ICU admission. Two analyses, using Cochran-Mantel-Haenszel statistics from PROC FREQ within SAS, will be performed at each time point. The first will use type of transplant (single or double) as a stratification factor and will use the following SAS code:

```
Proc freq data=data1 (where=(time=x)) noprint ;  
  table tran_typ*PGD*treat/cmh out=ct_typ ;  
  output out=cmh type cmh ;  
run ;
```

As the randomization did not include type of transplant it is possible that there will be insufficient data within each of the cells to perform the analysis. This will be assessed after the Month 1 database lock.

The second analysis will use center as a stratification factor.

Both analyses will be performed for both the ITT and PP populations. For each analysis, the number and percentage of patients within each table cell will be presented, together with the second of the three p-values provided by PROC FREQ (labeled as Row Mean Scores Differ), and the corresponding Mantel-Haenszel odds ratio and the associated 95% confidence interval.

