## 10 VALIDATION

All summary tables and figures will be validated by independent programming within SAS. Any numerical discrepancies will be resolved prior to finalization of the tables and figures. All outputs will have the following checks performed:

- Titles and footnotes are correct
- No errors or warnings in SAS log file
- Expected number of observations in dataset used for final output
- Matches the specifications documented in this plan

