### 13 TABLE SHELLS

Tables 2.1.x and 2.2.x Repeated Measurements Analysis

Tests of Fixed Effects				
Source	NDF	DDF	Type III F	P
Center	x	x	x.xx	0.xxxx
Time	x	x	x.xx	0.xxxx
Treatment	x	x	x.xx	0.xxxx
Center-by-treatment	x	x	x.xx	0.xxxx

Summary Statistics			
		Repertaxin	Placebo
Time=0	Least Squares Mean	xx.xx	xx.xx
	Mean	xx.xx	xx.xx
	SD	xx.xx	xx.xx
	Median	xx.xx	xx.xx
	Range	(xx.x; xx.x)	(xx.x; xx.x)
	N	x	x
Time=24	Least Squares Mean	xx.xx	xx.xx
	Mean	xx.xx	xx.xx
	SD	xx.xx	xx.xx
	Median	xx.xx	xx.xx
	Range	(xx.x; xx.x)	(xx.x; xx.x)
	N	x	x

Treatment Comparison					
Time	Comparison	Difference between Means	SE of difference	95% confidence interval	P-value
0	Repertaxin - Placebo	x.xxx	x.xxx	(-x.xx, x.xx)	0.xxxx
24	Repertaxin - Placebo	x.xxx	x.xxx	(-x.xx, x.xx)	0.xxxx

Table 2.3.x Analysis of PGD Score

	Repertaxin		Placebo		Odds Ratio [1]	95% CI for Odds Ratio	P-value [2]
	N	%	N	%			
Grade 0	xx	xx	xx	xx	x.xx	(x.xx, x.xx)	0.xxx
Grade 1	xx	xx	xx	xx			
Grade 2	xx	xx	xx	xx			
Grade 3	xx	xx	xx	xx			

[1] Odds ratio is Repertaxin:Placebo

[2] The p-value is obtained from a Cochran-Mantel-Haenszel test of the treatment difference.

Table 2.4.x Time to Freedom from Mechanical Ventilation

TIME POINT	Repertaxin				Placebo				Difference in Event Prob.	95% CI for Difference
	N=	Number of Patients Remaining	Cumulative Number of Events	Event Probability S.E.	N=	Number of Patients Remaining	Cumulative Number of Events	Event Probability S.E.		
24 hrs										
48 hrs										
72 hrs										
96 hrs										
etc										
Censored (N)	xx				xx				Chi-sq statistic	P-value
Log-rank										

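### PGD score: the printed code gives a P-value that ignores the order of the grades, and the promised Mantel-Haenszel odds ratio cannot be computed from a four-grade table

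*SAP*

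**What the plan says.** SAP section 9.5.2.2 plans two Cochran-Mantel-Haenszel (CMH) analyses of the PGD score at each of 0, 24, 48 and 72 hours, in both the ITT and PP populations. The first stratifies by transplant type and its code is printed: "table tran_typ*PGD*treat/cmh out=ct_typ". For the other, "The second analysis will use center as a stratification factor"; no code is printed.

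Each analysis reports cell counts and percentages with one P-value, specified thus: "together with the second of the three p-values provided by PROC FREQ (labeled as Row Mean Scores Differ". An effect measure is promised for both analyses as well: "and the corresponding Mantel-Haenszel odds ratio and the associated 95% confidence interval". SAP section 5 defines the score as an integer grade from 0 to 3. The shell for Tables 2.3.x in SAP section 13 has four grade rows, one odds ratio, one confidence interval and one P-value. Its footnotes say "Odds ratio is Repertaxin:Placebo" and "The p-value is obtained from a Cochran-Mantel-Haenszel test of the treatment difference".

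Protocol section 9.4.3 asks only for CMH statistics under the same two stratifications. It does not say which statistic, which scores or which odds ratio. Protocol section 4.2.1.2 lists the score under "Secondary efficacy (exploratory) endpoints".

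**The concern.** There are two separate faults.

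**P-value.** In a PROC FREQ request of the form stratum\*row\*column, *Row Mean Scores Differ* assigns scores to the columns and treats the rows as unordered groups. Here the rows are the PGD grades, so the test asks whether the mean treatment code differs among four unordered grades. A reader would take the label to mean a comparison of mean PGD grade between arms.

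**Odds ratio.** The Mantel-Haenszel common odds ratio is built from 2x2 strata. With four grades there is no single one, whichever variable is in the rows.

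The primary result is not at stake. But reduced PGD severity is the study objective, and the synopsis limits inferential testing of secondary endpoints to four measures, of which this is one. Validation may not catch the first fault: SAP section 10 checks that each output "Matches the specifications documented in this plan", and the variable order is part of the specification.

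**Working it through.** **Inputs.** Table order and chosen statistic: SAP 9.5.2.2. Four grades: SAP 5. Fifty per arm: SAP 3.2. Two-sided 5% by default: Protocol 9.4. The documents give no expected grade distribution, no single/double split and no power for PGD score, so those are assumptions below. The plan's only power figure (81% for 70 mmHg, SD 137, one-sided 0.05) reproduces at 81.4% with the noncentral t on 98 df. Steps 1 to 3 do not depend on it.

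**Step 1: degrees of freedom.** Row Mean Scores has R − 1 df and General Association has (R − 1)(C − 1).
- As printed (R = 4, C = 2): 3 df and 3 × 1 = 3 df. With two columns the two statistics are identical.
- Treatment in rows (R = 2, C = 4): Row Mean Scores has 1 df and equals the correlation statistic.

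The 3 df apply when all four grades occur at that time point.

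**Step 2: invented example, grades 0 to 3.** Stratum 1: repertaxin 8, 5, 1, 1; placebo 4, 4, 3, 4. Stratum 2: repertaxin 14, 10, 6, 5; placebo 9, 9, 8, 9.

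Treatment in rows: Q = [Σ(S − E)]² / ΣV, where S is the sum of grades on repertaxin, E its expectation, and V = n₁n₂/[n(n − 1)] × (sum of squares of the grades about their mean).
- Stratum 1: S − E = 10 − 16 = −6; V = 225/(30 × 29) × (70 − 32²/30) = 9.276.
- Stratum 2: S − E = 37 − 44.5 = −7.5; V = 1225/(70 × 69) × (201 − 89²/70) = 22.279.
- Q = 13.5²/31.555 = 5.776, 1 df, **P = 0.016**.

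Grades in rows, as printed: observed minus expected repertaxin counts by grade, summed over strata, are 4.5, 1.0, −2.0 and −3.5. The quadratic form gives Q = 5.855, 3 df, **P = 0.119**. This equals General Association and does not change when the grades are permuted. The correlation statistic is 5.776 (P = 0.016) in either order. A second invented table gave P = 0.136 as printed and 0.020 swapped.

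**Step 3: odds ratio.** The Mantel-Haenszel formula is Σ(ad/n) / Σ(bc/n), with a, b, c, d from 2x2 strata. The example must first be cut:
- grade ≥ 1: 3.633/8.133 = 0.45
- grade ≥ 2: 3.362/8.862 = 0.38
- grade ≥ 3: 2.224/5.724 = 0.39

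The answer depends on a cut-point that the plan does not name.

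**Step 4: power.** Simulation with 50 per arm and two-sided 5%; 40,000 runs per setting with a 30%/70% stratum split, except the last two rows (4,000 runs, 15 and 35 per arm).

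| Assumed setting | Treatment in rows, 1 df | As printed, 3 df |
|---|---|---|
| Placebo 30/30/20/20%, common odds ratio 2 | 46% | 31% |
| Same, 2.5 | 68% | 51% |
| Same, 3 | 82% | 68% |
| Same placebo, treated 30/45/20/5% | 32% | 52% |
| Same placebo, treated 30/50/5/15% | 22% | 62% |
| Mean ratio 315 vs 385, SD 137; infiltrates 75% in both arms | 23% | 28% |
| Same means and SD; infiltrates 75% placebo, 60% treated | 64% | 46% |

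Over six assumed placebo distributions and odds ratios from 2 to 3, the proportional-odds loss is 11 to 18 points. Type I error is 0.049 to 0.051 (1 df) and 0.047 to 0.049 (3 df). With eight equal center strata, if the printed order is reused, an odds ratio of 2.5 gives 68% against 51% (20,000 runs).

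**The case against.** The protocol asks only for a CMH test of treatment differences. A stratified 3-df test is a valid one, so the shell footnote remains literally true, and the mean-score intent is inferred from an output label. That is fair as to validity. But the SAP picks the second of three P-values, and in the printed order the second and third coincide. The choice makes sense only if mean scores were to be compared.

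The direction of the power effect is also open. Grade 0 against 1–3 depends on infiltrates alone, while grades 1–3 are split by PaO₂/FiO₂. The only effect the documents quantify is on PaO₂/FiO₂, and if infiltrate rates are equal at 75%, the 3-df test does slightly better. This stands: the power loss is conditional, and reversals are not confined to unusual shifts.

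A Mantel-Haenszel-type cumulative odds ratio for ordered categories does exist (0.41 on the example). The SAP does not specify it and the printed code does not produce it.

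Finally, the study is not pivotal, and the empty odds-ratio column would probably surface in programming before lock. That limits the consequence. It would still leave the cut-point or model to be chosen outside the plan.

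**Conclusion.** The concern holds on both counts. Followed exactly, SAP 9.5.2.2 yields an order-blind P-value for the transplant-type analysis and an odds-ratio column that cannot be filled for either analysis. The center-stratified P-value is affected only if the same variable order is used. The algebra is certain. The power figures rest on assumed grade distributions, infiltrate rates and stratum splits, and can go either way. The consequence is limited to a secondary, exploratory endpoint with type I error intact, but the plan should be corrected before lock.

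**What to change.** Amend SAP 9.5.2.2 and shell 2.3.x before database lock.

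1. **P-value.** Use `tran_typ*treat*PGD` and `center*treat*PGD` and keep *Row Mean Scores Differ* (1 df). Equivalently, name the first CMH P-value (correlation), which the printed request already yields. Print the center code as well.
2. **Effect measure.** Prespecify one: a common odds ratio with 95% CI from a proportional-odds model with the same stratification factor, or a Mantel-Haenszel odds ratio at one grade cut-point fixed now. State in the shell which odds are compared.

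The first change swaps two variable names or names a different P-value. The second needs one decision and up to 2 × 4 × 2 = 16 fits (stratifications, time points, populations). No new data are needed.

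There are downsides. Proportional odds may fit poorly because infiltrates and oxygenation define different boundaries, and a cut-point discards information. Either measure may occasionally disagree with the mean-score P-value in the same row. Center strata are sparse: about 100 patients over 8 centers, 4 grades and 2 arms average 100/64 ≈ 1.6 per cell. The 1-df test has less power for some shifts, including an oxygenation gain without fewer infiltrates.

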### 9.5.2.3 Time to freedom from mechanical ventilation

Time to freedom from mechanical ventilation will be derived as described in Section 5. Kaplan-Meier summary statistics and plots will be used to illustrate time to freedom from mechanical ventilation for each treatment group. The analysis will be performed using PROC LIFETEST within SAS:

```
proc lifetest plots=(s, ls, lls) data=data2 method=km outsurv=estimates ;  
  time freetime*censor(1) ;  
  strata treatment ;  
  ods output ProductLimitEstimates=file1 ;  
run ;
```

Patients who die while still on mechanical ventilation will be censored at the time of death.

The risk set and number of events occurring within each 12-hour interval will be presented together with the event probability and standard error. The estimated difference in event probability and corresponding 95% confidence interval will also be presented together with the log-rank and Wilcoxon tests for differences between treatments.

The analysis will also be performed by treatment and type of transplant.

Both analyses will be presented for both the ITT and PP populations.

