7.6. ICU DISCHARGE - HOSPITAL STAY

Date and time of ICU discharge will be recorded in the CRF, as well as vital status at ICU discharge. Every morning (@08:00) that a patient has not been discharged from the ICU, reasons for not discharging are recorded in the CRF.

Renal (CL_{cr}, urine output) and hepatic (bilirubin, transaminases) function will be tested at 12, 24, and 36 hours after the beginning of Investigation Product infusion.

Before hospital discharge, laboratory tests will be performed. Results will be recorded in the CRF.

Length of hospital stay, vital status at hospital discharge and AEs will be recorded.

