9.4. STATISTICAL METHODOLOGY

Appropriate descriptive statistics will be produced, according to the variable. For continuous data the mean, standard deviation, median and range (minimum and maximum) will be presented. For categorical data, frequencies and percentages will be presented. If appropriate, confidence intervals around the mean or the proportions will be presented.

All patient data collected on the CRF will be listed by patient, treatment group and center.

The data for the double-blind phase of the study (up to 30 days post-treatment) will be presented in the clinical study report. Data collected during the open phase of the study (from 1 month up to 12 months) will be presented in an addendum to the clinical study report.

Unless otherwise specified, the significance level used for statistical testing will be 5% and two-sided tests will be used.

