#### Duration of ICU stay

This is the interval in hours between ICU admission and ICU discharge and will be derived as: (date/time of ICU discharge – date/time of ICU admission)/3600. The result will be rounded to the nearest integer.

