#### 9.5.2.4 Duration of ICU stay

The duration of ICU stay will be derived as described in Section 5. This duration is equivalent to time to ICU discharge. The duration of ICU stay will be analyzed as described for time to freedom from mechanical ventilation.

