#### 9.5.2.5 Mortality

Frequency counts and percentages for the number of patients who die while in ICU and also the number and percentage of patients who die within the first 30 days post-transplant (derived as latest date of reperfusion + 30) will be presented by treatment group. This table will be presented for the ITT population only.

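### Censoring deaths makes the reported Kaplan-Meier probabilities overstate extubation alive and ICU discharge alive once any event follows a death, and an ICU death after extubation has no written rule

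*SAP*

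**What the plan says.** For time to freedom from mechanical ventilation, SAP 9.5.2.3 specifies one PROC LIFETEST call with a single censoring code. The only rule on death is: "Patients who die while still on mechanical ventilation will be censored at the time of death". The output is an event probability with its standard error by interval, and then: "The estimated difference in event probability and corresponding 95% confidence interval will also be presented together with the log-rank and Wilcoxon tests".

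SAP 9.5.2.4 carries this over: "The duration of ICU stay will be analyzed as described for time to freedom from mechanical ventilation". SAP section 5 derives the ICU duration without saying whether discharge must be alive: "This is the interval in hours between ICU admission and ICU discharge".

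The protocol adds two relevant statements. Section 7.6: "Date and time of ICU discharge will be recorded in the CRF, as well as vital status at ICU discharge". Section 4.2.1.2: "ICU mortality, defined as vital status at the ICU discharge". Protocol 9.4.3 plans Kaplan-Meier plots and a Median test for both durations and gives no rule for death.

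Deaths are reported separately. SAP 9.5.2.5 plans, by arm, "Frequency counts and percentages for the number of patients who die while in ICU", together with 30-day deaths. The shell for Table 2.4.x prints, per arm, N, patients remaining, cumulative events, event probability and the number censored.

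**The concern.** Censoring assumes that the patient could still have the event later, at the rate seen in those who remain. That is false for a death. Kaplan-Meier passes the dead patient's weight to the survivors, so the printed figure is not the share of the arm that came off the ventilator, or left the ICU, alive. A reader will nevertheless take it that way.

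These are two of the four secondary endpoints that receive inferential tests (Protocol synopsis, Statistics). If more patients die in one arm, the two curves can agree although fewer patients in that arm were extubated or discharged alive. The plan does penalise death elsewhere: in the sensitivity analysis of the PaO2/FiO2 ratio, a patient who dies within 24 hours is given the value zero.

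For ICU stay there is a second gap. The inherited rule covers only deaths on the ventilator, so a patient who dies in the ICU after extubation has no stated coding.

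**Working it through.** The plan states no figure for ventilation time or ICU stay, so there is none to reproduce. Its power figures concern the PaO2/FiO2 ratio only. All mortality, weaning and ICU rates below are assumptions.

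**1. Direction.** At event time t_j let d_j patients have the event out of n_j at risk.
- SAP estimate: 1 − KM(t) = Σ K(t_j−)·d_j/n_j, where K is the product of (1 − d/n) over earlier event times only.
- Cumulative incidence: CIF(t) = Σ G(t_j−)·d_j/n_j, where G also falls at each death.

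G ≤ K always, and G < K after the first death. So 1 − KM is never below CIF, and it exceeds CIF as soon as one event follows a death. If no event follows a death, the excess is zero. This needs no outside figure.

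**2. Size at day 7 (168 h).** Assume ventilation times are 70% exponential with mean 36 h and 30% exponential with mean 168 h. A fraction p is set to die at a time D, uniform on 12–72 h and unrelated to weaning.
- S(168) = 0.7·e^(−168/36) + 0.3·e^(−1) = 0.0066 + 0.1104 = 0.1169. The SAP estimate therefore tends to 88.3%, whatever p is.
- E[S(D)] = 0.7·(36/60)·(e^(−12/36) − e^(−72/36)) + 0.3·(168/60)·(e^(−12/168) − e^(−72/168)) = 0.2441 + 0.2349 = 0.4790.
- Ventilator deaths = 0.4790·p.
- Extubated alive = 0.8831 − p·(0.4790 − 0.1169) = 0.8831 − 0.3620·p.

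| p | ventilator deaths | SAP estimate | extubated alive | excess (points) |
|---|---|---|---|---|
| 5% | 2.4% | 88.3% | 86.5% | 1.8 |
| 10% | 4.8% | 88.3% | 84.7% | 3.6 |
| 20% | 9.6% | 88.3% | 81.1% | 7.2 |
| 30% | 14.4% | 88.3% | 77.4% | 10.9 |

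Simulation of the same model in whole hours agrees to about 0.1 point.

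A second set of assumptions uses one arm of 50, survivors' median 48 h, and deaths spread over 12–240 h (1 − KM v CIF):

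| deaths | 72 h | 168 h | 30 days |
|---|---|---|---|
| 3 (6%) | 61.1 v 60.0 | 88.6 v 86.0 | 100 v 94 |
| 5 (10%) | 59.1 v 58.0 | 85.7 v 82.0 | 100 v 90 |
| 10 (20%) | 53.7 v 52.0 | 77.7 v 72.0 | 100 v 80 |

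**3. Difference between arms.** With identical weaning and p = 20% v 5%, the SAP estimates are 88.3% v 88.3%, a difference of 0. Extubated alive is 81.1% v 86.5%, a difference of 5.4 points. With 2 v 6 deaths per 50 and a 48 h median, the Kaplan-Meier difference is 5.5 points at 168 h and 0 at 30 days. The CIF difference is 8.0 at both; at 30 days this is 48/50 − 44/50.

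**4. Tests.** The protocol default applies: "Unless otherwise specified, the significance level used for statistical testing will be 5% and two-sided tests will be used". That is nominally 2.5% per direction. In 4,000 simulated trials of 50 per arm, with p = 5% in both arms and deaths censored, the log-rank test was significant in 2.4% and 2.8% in the two directions. With p = 20% v 5%, it favoured the arm with more deaths in 2.8%. The simulation error is √(0.025·0.975/4000) = 0.25 points, so these rates are about nominal.

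**5. ICU stay.** Assume 50 patients, a 96 h median, 5 ventilator deaths, and 3 ICU deaths after extubation. At 336 h the planned method gives 86.8% if the 3 are coded as discharges and 83.9% if they are censored. Discharged alive is 76.0%. Both codings overstate.

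**6. Check of the fix.** With p = 20% in 400,000 patients the true value is 81.2%. Keeping deaths in the risk set to the longest follow-up gives 81.2% with no other early censoring, 81.0% with 2.5% withdrawn before the event, and 80.6% with 10% withdrawn. A competing-risk estimator gives 81.2% each time. The SAP rule gives 88.3–88.4%.

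**The case against.** The strongest defence is that the table already carries the correction. The 2.4.x shell prints N and cumulative events per arm, and their ratio is the crude proportion extubated. With no other early censoring that ratio is the cumulative incidence. This stands as mitigation, but the probability, difference and CI that the table reports still rest on the death-censored estimate.

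Second, the size is assumed and modest against the trial's precision. With 50 per arm at about 85%, the 95% CI for a difference is ±1.96·√(2·0.85·0.15/50), or about ±14 points. Similar mortality in both arms largely cancels in the difference. This also stands, and it limits the importance of the point.

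Third, a reader might infer that the log-rank and Wilcoxon tests are invalid or favour the arm with more deaths. The documents do not support that. Both tests compare the rate of extubation or discharge among patients still at risk. A clear departure (6.3% in the wrong direction by log-rank) appeared only in an extreme assumed case: early deaths of 15.7% v 3.9%, all in slow weaners. No figure in the documents supports that case. Keeping deaths as never extubated raises detection of the arm with more deaths (p = 20% v 5%) from 3.0% to 13.4% by log-rank and to 5.5% by Wilcoxon. But this mixes weaning with mortality, which has its own endpoints.

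Fourth, a reader might infer that the plan counts ICU deaths as discharges. It does not say so. Recording vital status at ICU discharge makes that coding possible, but censoring is the more natural parallel with the ventilation rule. The gap is only that no rule is written.

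**Conclusion.** The point holds for the reported probabilities, their difference and the 95% CI. The direction is certain: they are never below the proportion extubated or discharged alive, and are above it once any event follows a death. The size is not known from the documents. Under the assumed weaning model it is about 2 points at 2.4% ventilator deaths, 3.6 at 4.8% and 7 at 9.6%. It is nil if no event follows a death. The between-arm difference is misleading mainly when mortality differs between arms.

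The point does not extend to the tests, which answer a valid cause-specific question. Nor does it mean that deaths are hidden: they appear in the mortality table, the adverse event tables and the death listing. The unwritten rule for an ICU death after extubation is a real gap, and either coding would overstate discharge alive. Both endpoints are exploratory and no primary conclusion changes. It is still worth correcting before database lock, because a stated rule produces figures that do not mean what a reader will take them to mean.

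**What to change.** In SAP section 5, define the two events as extubation alive and ICU discharge alive. State that an ICU death is never a discharge event, whatever date stands in the discharge field.

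In SAP 9.5.2.3 and 9.5.2.4, report the event probabilities, their difference and the 95% CI as cumulative incidence with death as a competing event. If no patient is censored early for another reason, the existing code gives the same estimate once each death before the event is kept in the risk set to the longest follow-up across both arms. If any patient is censored earlier, for example by withdrawal, for which the section gives no rule, use a cumulative incidence estimator.

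Keep the planned log-rank and Wilcoxon tests on the death-censored data, labelled as comparing the cause-specific rate. A test with deaths kept as never having the event may be added as supportive.

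Cost: SAP wording plus some reprogramming and independent validation of up to eight tables (2.4.1–2.4.4, 2.5.1–2.5.4) and eight figures (1.1–1.4, 2.1–2.4). No new data are needed: extubation time, ICU discharge time, vital status and the death report are already collected. The event probabilities will look slightly lower.
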